5.1.5 Visit 9 (wk23) – Only MOD-4023 Dose Cohorts

This visit will take place **exactly** one week (7 days) after MOD-4023 dosing, prior to administration of the next dose. If patient is unable to attend the visit, the entire visit can be postponed by one week in order to obtain pre-dose levels of MOD-4023 and IGF-I+IGFBP-3.

The following assessments will be performed prior to MOD-4023 dosing:

1. Physical examination and vital signs (prior to blood sampling);
2. AEs, local tolerability, and concomitant medications (prior to blood sampling);

OPKO Biologics	Protocol for Clinical Study CP-4-004	Page 56 of 133
Effective Date: Date of final electronic approval		

3. PD: IGF-I and IGFBP-3 serum levels (prior to dosing);
4. MOD-4023 (cohort 1-3) serum levels (prior to dosing);
5. MOD-4023 dosing.

The following procedures will be performed **after MOD-4023 dosing**:

1. Vital signs: 30 min, 2 hours (± 20 min), and 4 hours (± 20 min) post dose.
2. Injection site reaction: 30 min and 4h (± 20 min) after injection.

5.1.6 Visit 10 (wk26) – All Cohorts

The following assessments will be performed:

1. Physical examination and vital signs;
2. AEs, local tolerability, and concomitant medications;
3. Parameters of glucose metabolism: fasting glucose, insulin, HbA1c;
4. Other hormonal levels: TSH, free T4, free T3, cortisol;
5. Antigenicity: anti MOD-4023 antibodies/anti-hGH antibodies;
6. Routine safety biochemistry, hematology and urinalysis parameters;
7. Patient's height;
8. Patient's weight;
9. Fundoscopy;
10. Parameters of lipid metabolism (with Lp(a) lipoprotein);
11. Pubertal status;
12. PD: IGF-I and IGFBP-3 serum levels;
13. MOD-4023 (cohort 1-3) and Genotropin (cohort 4) levels;
14. Adjustment of dose to patient's weight.

After completion of visit 10, each patient will be assessed separately, for the growth progress and overall safety. If the growth meets pre-determined criteria¹, and there are no safety concerns, the patient will continue with the same dose.

5.1.7 V11 (month 9), V12 (month 12) – All Cohorts – PERIOD II

This period will consist of 2 visits at Months 9 and 12. Month 9 visit will be conducted on day 4(-1) after MOD-4023 dosing for MOD-4023 dose cohorts, and any day during the week for

¹ Delta height SDS at least 0.2

OPKO Biologics	Protocol for Clinical Study CP-4-004	Page 57 of 133
Effective Date: Date of final electronic approval		

Genotropin cohorts. Month 12 visit (final visit of the Main Study) will be conducted 4 days (-1) after the last MOD-4023 dose for MOD-4023 cohorts and the day after the last Genotropin dose for Genotropin cohorts. Period II assessments will include the following at each visit:

1. Physical examination and vital signs;
2. AEs, local tolerability, and concomitant medications;
3. Parameters of glucose metabolism: fasting glucose, insulin, and HbA1c;
4. Other hormonal levels: TSH, free T4, free T3, cortisol;
5. Antigenicity: anti MOD-4023 antibodies/anti-hGH antibodies (only month 12 visit);
6. Routine safety biochemistry, hematology, and urinalysis parameters;
7. Patient's height;
8. Patient's weight;
9. Parameters of lipid metabolism at both visits (with Lp(a) lipoprotein at month 12 only);
10. Pubertal status (only month 12 visit);
11. PD: IGF-I and IGFBP-3 serum levels;
12. MOD-4023 (cohort 1-3) and Genotropin (cohort 4) serum levels;
13. Fundoscopy (Month 12 only or earlier if there are signs or symptoms indicative of benign intracranial hypertension);
14. ECG (Month 12 only);
15. Bone age (Month 12 only).

At the end of Period II, a formal data analysis of all endpoints will be performed.

5.2 12-MONTH OPEN LABEL EXTENSION (OLE) PERIOD III

Visits (Visit 1 OLE/Day 1, Visit 2 OLE/Month 1, Visit 3 OLE/Month 3, Visit 4 OLE/Month 6, Visit 5 OLE/Month 9 and Visit 6 OLE/Month 12)

Patients who completed 12 months of treatment in the Main Study will be eligible to continue to a 12-month OLE period. Patients who received MOD-4023 in the Main Study (initial 12 months of active treatment) will continue to receive MOD-4023; dose will be same as in the Main Study. For these patients, study visits will take place every 3 months, starting at visit 3 OLE.

For these patients, V12 of the Main study will be considered as the first visit of the OLE phase in which the patient will receive the study drug for the next 3 months of the OLE.

Patients who received active comparator, Genotropin, during the Main Study, will be switched to MOD-4023 (will be randomized to one of the three MOD-4023 cohorts). Their visit schedule during the first three months of the OLE will be as follows: Visit 1 OLE for the first MOD-4023 injection and training of MOD-4023 administration (week 52 +1 day, which is

OPKO Biologics	Protocol for Clinical Study CP-4-004	Page 58 of 133
Effective Date: Date of final electronic approval		

on Month 12 visit of the Main Study), Visit 2 OLE will be 28 days + 4 (-1) days after the first MOD-4023 injection and Visit 3 OLE will be 3 months after first MOD-4023 injection (i.e. 13±2 weeks + 4 (-1) days after the first MOD-4023 injection). All subsequent visits will be every three months (i.e. every 13±2 weeks, 4 days (or 3 days, when necessary) after dosing).

Patients who are off treatment for over XXXXXXXXXX between the last MOD-4023/Genotropin dose in the Main Study and the first OLE dose (2nd year) will be allowed to continue into the OLE period after the following tests will be conducted:

- Parameters of glucose metabolism: fasting glucose, insulin, and HbA1c
- Antigenicity: anti MOD-4023 antibodies (only Genotropin group – baseline for future tests)
- Routine safety laboratory (biochemistry, hematology, and urinalysis)
- PD: IGF-I and IGFBP-3 baseline serum levels
- MOD-4023 baseline serum levels

In the 12-month OLE visit (the second year of treatment) the following assessments will be included at each visit (unless otherwise specified):

- Adjustment of dose for weight
- local tolerability
- Physical examination and vital signs;
- AEs, and concomitant medications;
- Parameters of glucose metabolism: fasting glucose, insulin, and HbA1c;
- Other hormonal levels: TSH, free T4, free T3, cortisol;
- Antigenicity: anti MOD-4023 antibodies (only once every 6 months);
- Routine safety laboratory (biochemistry, hematology, and urinalysis);
- Patient's height;
- Patient's weight;
- Parameters of lipid metabolism;
- Lp(a) lipoprotein (only once at Month 12 OLE);
- Pubertal status (only once at Month 12 OLE);
- PD: IGF-I and IGFBP-3 serum levels;
- MOD-4023 serum levels;
- Fundoscopy (once at Month 12 OLE, or earlier if there are signs or symptoms indicative of benign intracranial hypertension);
- ECG (only once at Month 12 OLE)

OPKO Biologics	Protocol for Clinical Study CP-4-004	Page 59 of 133
Effective Date: Date of final electronic approval		

- Bone age (only once at Month 12 OLE);
- Dispensing of drug and return of used drug
- Patient diary dispensing and return of completed patient diaries

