Physical examination, vital signs, AEs, local tolerability, concomitant medications, parameters of glucose metabolism (fasting glucose, insulin and HbA1C), other hormonal levels (TSH, free T4, free T3, cortisol), antigenicity (anti MOD-4023 antibodies for cohort 1-3 patients and anti r-hGH antibodies for cohort 4 patients), routine safety biochemistry and hematology, patient's height and weight, parameters of lipid metabolism, pubertal status, IGF-I and IGFBP-3 serum levels, fundoscopy.

During Period I, the dose of MOD-4023 and r-hGH will be adjusted to the patient's body weight every three months. Doses may be decreased for safety reasons according to the pre-defined dose-adjustment criteria (which will be based on the severity of AEs or elevated levels of IGF-I). For patients on MOD-4023, the dose may be decreased based on repeated day 4 levels of IGF-I above +2.0 SDS. For patients on Genotropin, the dose may be decreased based on repeated IGF-I levels above +2.0 SDS.

The study Medical Monitor shall review all AEs from entries in the e-CRF on a weekly basis and all SAE safety reports as received. The key safety data will be reviewed by an independent DSMB approximately every 6 months or on an ad-hoc basis if any safety concerns arise. After completion of Period I each patient will be assessed separately for the growth progress and overall safety. If the growth meets the pre-defined criteria¹ and there are no safety concerns, the

¹ Delta Height SDS at least 0.2

OPKO Biologics	Protocol for Clinical Study CP-4-004	Page 10 of 133
Effective Date: Date of final electronic approval		

patient will continue with the same dose, otherwise dose modifications will be performed according to the pre-determined rules.

PERIOD II: SIX MONTH CONTINUOUS DOSING PERIOD

The purpose of Period II is to collect an additional 6 months of efficacy and safety data. During period II, patients will be kept whenever it is possible on the originally allocated dose levels; however, the dose may be adjusted for safety reasons throughout the study and/or for efficacy reasons after 6 months of dosing. Patients allocated to the r-hGH dose group will continue their doses as initiated earlier, up to the end of the 12-month treatment period.

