5.1.2 Visit 1 – All Patients

This visit will take place in the medical center for all patients on the day of the first dose. The following procedures will be performed (prior to dosing for MOD-4023 cohorts):

1. Physical examination including height and weight;

¹ Central laboratory results will be used for eligibility confirmation.

OPKO Biologics	Protocol for Clinical Study CP-4-004	Page 49 of 133
Effective Date: Date of final electronic approval		

2. Vital signs (within one hour prior to dosing);
3. AEs, local tolerability;
4. Concomitant medications;
5. Parameters of glucose metabolism (fasting glucose, insulin, and HbA1C);
6. Other hormonal levels (TSH, free T4, free T3, cortisol);
7. Baseline antigenicity (anti MOD-4023 antibodies for cohort 1-3 patients) and anti hGH for Genotropin patients
8. Routine safety biochemistry and hematology;
9. Parameters of lipid metabolism (with Lp(a) lipoprotein);
10. IGF-I and IGFBP-3 serum levels, baseline MOD-4023 (cohorts 1-3) and Genotropin (cohort 4) levels;
11. Training for parents or legal guardians on drug administration.

Patients allocated to the MOD-4023 cohorts will be administered the first dose by the study staff in the morning hours, after completion of all of the above.

The following procedures will be performed after dosing (for MOD-4023 cohorts):

1. Vital signs: 30 min, 2 hours (± 20 min) and 4 hours (± 20 min) post dose;
2. Injection site reaction: 30 min and 4h (± 20 min) after injection.

Patients allocated to the Genotropin cohort will be administered the first dose at home in the evening hours.

5.1.3 PK/PD Visits (V2 - Week 2; V3 - Week 4; V4 -Week 6)

All patients randomized to receive one of the three MOD-4023 doses will start treatment for 2 weeks with the low MOD-4023 dose (0.25 mg protein/kg). Based on the patient's dose allocation, this will be followed by a dose increase to the next dose level every two weeks until the final allocated dose is reached (see [Table 5](#)).

Subsequent to the second dose administration of the targeted dose, limited (population based) PK and PD sampling will be taken (according to [Table 6](#) and [Table 7](#)).

Patients allocated to a MOD-4023 dose cohort (cohorts 1-3) will be randomized within the cohort into one of three blocks and undergo limited PK/PD sampling (4 samples per patient over a period of one week), according to [Table 6](#) below.

OPKO Biologics	Protocol for Clinical Study CP-4-004	Page 50 of 133

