5.7.1.5 Assessment of antigenicity

Immunogenicity of MOD-4023 and of r-hGH will be assessed.

Baseline data for anti-hGH will be collected at Screening, and no patients with positive anti-hGH antibodies will be included in the study. Baseline anti-MOD levels will be measured at Visit 1. During the treatment period, samples will be taken according to the schedule in [Appendix 1: Schedule of Assessments – Main Study](#) to [Appendix 5](#).

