Appendix 1: Schedule of Assessments – Main Study

Main Study	Screening	Treatment Period													
		Period I													
		Months 1-6													
		≤6 weeks	W1 (V1)	W2* (V2)	W3	W4* (V3)/ [M]	W5	W6* (V4)	W10 (V5)	W14 (V6)	W 18 (V7)	W22 (V8)	W23 (V9)/ [M]	W26 (V10)	Month 9 (V11)
Informed consent/Assent	X														
Medical history	X														
Previous and concomitant medication	X								Throughout the study						
Demography	X														
Growth history	X														
Actual height	X	X													
Body weight	X	X													
Physical examination	X	X	X												
Vital signs ²	X	X ⁵	X ⁵												
Injection Site Reaction (local tolerability)			M ⁶	X ⁶											
ECG	X														X
Pubertal status (Tanner)	X														X
Bone age (Greulich-Pyle)	X														X
Karyotype in girls	X														
SHOX evaluation	X														
GH stimulation tests ⁷	X														
Routine safety biochemistry/hematology and urinalysis	X	X													
IGF-I and IGFBP-3	X	X	According to sampling tables at the end of this appendix					X	X	X	X	M	X	X	X
MOD-4023 levels		M	According to sampling tables at the end of this appendix					M	M	M	M	M	M	M	M

OPKO Biologics	Protocol for Clinical Study CP-4-004	Page 110 of 133
Effective Date: Date of final electronic approval		

Main Study	Screening	Treatment Period															
		Period I													Period II		
		Months 1-6													Months 7-12		
X – Done in all Cohorts	≤6 weeks	W1 (V1)	W2* (V2)	W3	W4* (V3)/ [M]	W5	W6* (V4)	W10 (V5)	W14 (V6)	W (V7)	W22 (V8)	W23 (V9)/ [M]	W26 (V10)	Month 9 (V11)	Month 12 (V12)		
G – Done in (Genotropin) Cohort 4																	
Genotropin levels		G	According to sampling tables at the end of this appendix						G	G	G	G		G	G	G	
Anti-MOD- 4023 antibodies		M												M		M	
Anti-hGH antibodies	X	G												G		G	
Thyroid status (free T4, free T3, TSH)	X	X								X				X	X	X	
Cortisol levels	X	X								X				X	X	X	
Standard dose short ACTH test ³	X																
Fasting glucose, fasting insulin	X	X	X											X	X	X	
HbA1C	X	X												X	X	X	
Lipid panel	X ⁸	X ⁸									X	X ⁸	X	X	X ⁸	X	X ⁸
AE assessment														Throughout the study			
Fundoscopy	X													X ⁴		X ⁴	
MRI	X																
MOD-4023 administration		M	M											M		M ⁹	
Genotropin administration				G												G ¹⁰	
Training for study medication administration	X	X															
Hand-out of study medication			X	X										X	X		
Hand-out of patient diary			X	X										X	X		

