Appendix 2: Schedule of Assessments – 12-Month Open Label Extension (OLE) – Period III

Assessments	OLE visit #	FIRST YEAR OLE STUDY MONTH					
		follow up Visit ¹	Day 1 & Month 1 ²	Month 3	Month 6	Month 9	Month 12
		Visit 0	Visits 1-2	Visit 3	Visit 4	Visit 5	Visit 6
Previous and concomitant medication			X	X	X	X	X
Actual height			X	X	X	X	X
Body weight			X	X	X	X	X
Physical examination			X	X	X	X	X
Vital signs			X	X	X	X	X
Injection Site Reaction (local tolerability)			X	X	X	X	X
ECG							X
Pubertal status (Tanner)							X
Bone age (Greulich-Pyle)							X
Routine safety biochemistry/hematology and urinalysis		X	X	X	X	X	X
IGF-I and IGFBP-3		X	X	X	X	X	X
MOD-4023 serum levels		X	X	X	X	X	X
Anti-MOD-4023 antibodies		X ³			X		X
Thyroid status (free T4, free T3, TSH)			X	X	X	X	X
Cortisol levels			X	X	X	X	X
Fasting glucose, fasting insulin		X	X	X	X	X	X
HbA1C		X	X	X	X	X	X
Lipid panel			X	X	X	X	X
Lipoprotein							X
AE assessment			X	X	X	X	X
Fundoscopy							X ⁴
MOD-4023 administration			X				
Training for study medication administration			X				
Dispense study medication		X	X	X	X	X	X
Dispense patient diary		X	X	X	X	X	X
Return and accountability of study medication			X	X	X	X	X
Return and review of patient diary			X	X	X	X	X

¹ Applicable only to patients who were off-treatment for over XXXXXXXXXX between Main Study Month 12 and Visit 1 OLE.

² Applicable only to patients who received Genotropin in the Main Study and switched to MOD-4023 will attend the following visits:

Day 1 is Month 12 visit of the Main Study in which the patient will be trained on medication administration and Visit 2/OLE will be 28 days + 4 (-1) days after the first MOD-4023 injection.

³ Applicable for Genotropin patients

⁴ Earlier if there are clinical signs of intracranial hypertension.

OPKO Biologics	Protocol for Clinical Study CP-4-004	Page 114 of 133
Effective Date: Date of final electronic approval		

Appendix 3: Schedule of Assessments – Long-Term OLE (LT-OLE) Period IV from Second Year of OLE/Third Year of Treatment until switch to LT-OLE-PEN period

Assessments	follow up Visit ¹	First Month 3 visit ² (on day 3 or 4 post-dosing)	Early termination visit ³	LT OLE visits by Month over each year until switch to LT-OLE-PEN period				
				Month 3 visit	Month 6 visit	Month 9 visit	Month 12 each year and End of Study Visit	
Visit 0	Visit 1a	On Dosing Day	day 4 (-1) post dose	day 4 (-1) post dose	day 4 (-1) post dose	day 4 (-1) post dose	On Dosing Day	day 4 (-1) post dose

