9.2 Antibodies

Anti-somatrogon antibody (ADA), anti-somatrogon neutralizing antibody, and anti-hGH neutralizing antibody will be tested at month six and month 12 in Period III and then every six months thereafter. The results of the antibody testing will be summarized for each test at each of the OLE and PEN time points tested. The titer and specificity (anti-hGH and CTP) of confirmed ADA will be summarized. The anti-somatrogon and anti-hGH neutralizing antibody status (positive or negative) are only assessed when a patient is confirmed positive for ADA, so any sample that has not shown somatrogon specificity will be considered negative for NAb. The numeric values for titer will be summarized by median, min and max.

Overall incidence of TEAEs and injection site reactions will also be summarized by ADA status.

HV, HT SDS, and peak IGF-1 SDS will be summarized for each reporting period by ADA status.

ADA status will be assigned on a rolling or dynamic basis. A patient is only considered ADA positive at the beginning of the year in which they test positive and for the remainder of the study.

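### Genotropin children who switch to MOD-4023 without a treatment gap have no scheduled anti-MOD-4023 sample before their first dose, and SAP 9.2 has no baseline rule, so the incidence of antibody formation can include antibodies already present

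*Protocol*

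**What the plan says.** **Main Study.** Protocol section 5.1.2 lists at Visit 1 "Baseline antigenicity (anti MOD-4023 antibodies for cohort 1-3 patients) and anti hGH for Genotropin patients". The synopsis makes the same split for Period I: "antigenicity (anti MOD-4023 antibodies for cohort 1-3 patients and anti r-hGH antibodies for cohort 4 patients". Appendix 1 codes each row by cohort, with the key "G – Done in (Genotropin) Cohort 4". Its anti-MOD-4023 row carries M marks only. Its anti-hGH row carries X at screening and G afterwards.

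Three places name no cohort. Sections 5.1.6 and 5.1.7, both headed for all cohorts, give the two assays separated by a slash; the Month 12 entry reads "Antigenicity: anti MOD-4023 antibodies/anti-hGH antibodies (only month 12 visit". Section 5.7.1.5 says "Baseline anti-MOD levels will be measured at Visit 1".

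**Switch.** Under section 5.2 a Genotropin child receives the first MOD-4023 injection at OLE Visit 1, which is the Main Study Month 12 visit. The same section lists, among the tests for patients with a treatment gap, "Antigenicity: anti MOD-4023 antibodies (only Genotropin group – baseline for future tests". In Appendix 2 the anti-MOD-4023 row is marked at Visit 0 (footnoted to Genotropin patients), Month 6 and Month 12, and is blank at Visits 1-2. The Visit 0 footnote begins "Applicable only to patients who were off-treatment for over" and continues with a redacted interval.

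**SAP** (where MOD-4023 is called somatrogon). Section 9.2 says the antibodies "will be tested at month six and month 12 in Period III and then every six months thereafter", and the Period III flow chart in section 4.3 agrees. ADA status is rolling: a positive test makes the child positive from the start of that year until the end of the study. No baseline enters the rule. Section 9.2 also summarises the titer and the specificity (hGH or CTP) of confirmed ADA. Section 3.2.1 lists incidence of antibody formation as a safety endpoint.

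**The concern.** Formation of antibodies is a change from absent to present, so it needs a sample from before exposure. Cohorts 1-3 have one at Visit 1. The protocol sees the same need for Genotropin children, since section 5.2 labels their sample as a baseline, but ties it to an interruption of treatment. The need comes from first exposure to MOD-4023, with or without an interruption.

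MOD-4023 is hGH fused to CTP (section 1.2), so an anti-hGH antibody raised during the Genotropin year could bind in the anti-MOD-4023 assay. At OLE Month 6 it would look like a new somatrogon antibody. Under SAP 9.2 that child becomes ADA-positive from the start of OLE year 1, the day of the first MOD-4023 dose, and stays so. At stake is one named safety endpoint in an analysis whose primary objective is safety (SAP 3.1.1).

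**Working it through.** There is no figure in the plan to reproduce. The check is a trace of every scheduled antibody sample for a Genotropin child who switches without a gap.

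| Time | Anti-hGH | Anti-MOD-4023 | Source |
|---|---|---|---|
| Screening | yes; positives excluded | no | 4.2, 5.7.1.5, Appendix 1 |
| Visit 1 | yes | no | 5.1.2, Appendix 1 |
| Week 26 | yes | no | 5.1.6 read with Appendix 1 |
| Month 12 = OLE Visit 1, first MOD-4023 dose | yes | no | 5.1.7 read with Appendix 1; Appendix 2 |
| OLE Month 1 | no | no | Appendix 2 |
| OLE Month 6 | only as specificity of a confirmed ADA | **yes, the first** | Appendix 2; SAP 4.3, 9.2 |

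A switcher with a gap differs in one cell: Visit 0 adds an anti-MOD-4023 baseline.

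**What a positive result at Month 6 can mean.** Section 6.1.3 describes Genotropin as having the same amino acid sequence as pituitary hGH. Section 1.2 says MOD-4023 adds CTP to hGH.

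- *CTP-specific ADA:* not expected to arise from Genotropin. Reactivity to CTP before the first dose was never tested in these children, so it is not excluded.
- *hGH-specific ADA, Month 12 anti-hGH negative:* supports formation on MOD-4023, through a different assay.
- *hGH-specific ADA, Month 12 anti-hGH positive:* the antibody may date from the Genotropin year; emergence is not confirmed.

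SAP 9.2 holds no rule that uses the Month 12 result or the specificity in this way.

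**Size.** Inputs: up to 56 patients, up to 14 per cohort (protocol synopsis); 53 entered the OLE (SAP 4.1).

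- Upper bound on children affected: 14/56 = 25% of those planned; 14/53 = 26% of those in the OLE.
- Effect of one child wrongly counted: 1/53 = 1.9 percentage points overall; 1/14 = 7.1 points among switchers.
- Chance that at least one of 14 switchers had reactivity before the first dose, at an **assumed** prevalence p (the documents give none), from 1 − (1 − p)^14:

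| p | 1% | 2% | 5% | 10% |
|---|---|---|---|---|
| Chance | 13% | 25% | 51% | 77% |

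These chances assume that 14 children switched and none had a gap.

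**The case against.** **Attribution is not lost.** A reader might infer that antibodies found at OLE Month 6 cannot be attributed to MOD-4023 at all. The documents do not support that. Anti-hGH positives are excluded at screening, anti-hGH is scheduled on the day of the switch, and SAP 9.2 reports specificity. Together these settle much of the question. This part of the objection stands. What remains is that the anti-MOD-4023 assay itself cannot confirm emergence of an hGH-specific ADA, that prior CTP reactivity is untested, and that no SAP rule turns the available data into a classification.

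**The tables by ADA status are not spoiled.** A reader might also infer that the error runs into every such table. It does not. Those tables compare growth, IGF-1 and adverse events between children with and without a detected antibody. A child who carries a confirmed antibody binding MOD-4023 belongs in the positive group whichever product raised it. Origin matters for the incidence-of-formation endpoint.

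**The looser wording might supply the sample.** Sections 5.1.6 and 5.1.7 could be read as giving every cohort both assays, the more so because the drug-level item in the same lists does split by cohort. Section 5.1.2, the synopsis and Appendix 1 all split antigenicity by cohort, so the slash most likely means one assay or the other. Section 5.7.1.5 would not help even if read broadly: Visit 1 falls a year before the switchers' first MOD-4023 dose. These passages need to be reconciled, and the laboratory data checked for any Month 12 anti-MOD-4023 results in cohort 4.

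**A quarter is a ceiling.** The number of switchers, the number with a gap and the gap limit are not available. No document reports an actual carry-over antibody.

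**Conclusion.** The schedule gap is real, and its consequence is limited. For Genotropin children who switched without a gap, no anti-MOD-4023 sample is scheduled before the first MOD-4023 dose, and SAP 9.2 assigns ADA status with no baseline. The reported incidence of anti-somatrogon antibody formation can therefore include antibodies that predate MOD-4023. The issue covers at most 14 of 53 OLE patients and moves the overall incidence by 1.9 points per child wrongly counted. Cohorts 1-3 have a Visit 1 sample, so for them only the rule is missing.

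This rests on reading the slash in sections 5.1.6 and 5.1.7 through Appendix 1, and on the cap of 14 per cohort having held. It does not invalidate the study. It should be corrected because the remedy uses results already scheduled.

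**What to change.** 1. **SAP 9.2, incidence endpoint only.** Count an ADA as treatment-emergent only if the last sample before MOD-4023 was negative or the titer rose from it. State in advance what counts as a rise; the documents give no threshold.
2. **Switchers without an anti-MOD-4023 baseline.** Classify them from the Month 12 anti-hGH result together with the hGH or CTP specificity of the ADA, as set out in the three cases above. Report them on their own line, marked as having no anti-MOD-4023 baseline.
3. **Retained serum.** If Month 12 serum was kept, which the documents do not say, run the anti-MOD-4023 assay on it.
4. **Protocol text.** Reconcile sections 5.1.6, 5.1.7 and 5.7.1.5 with Appendix 1 by naming cohorts, and section 5.2 with Appendix 2 on which Genotropin patients have the baseline.
5. **No change** to the tables of growth, IGF-1 and adverse events by ADA status.

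Adding a pre-dose sample to Appendix 2 would now reach nobody: SAP 4.1 and 4.2 describe OLE entry and the re-randomisation of Genotropin patients as completed.

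Items 1 and 2 need a short SAP paragraph and one extra table line, with no new blood. Item 3 is at most 14 assays. The downside is that a few switchers will be shown as baseline unknown.
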